### Deaths

### Quality Management

Quality management reviews are performed annually and were last completed on xxxx.

## 2. Protocol Synopsis

Planned Accrual: N= 128; approximately 60-70 CRS/HIPEC procedures are performed annually at UCSD.

Study Design: The proposed study is a prospective, randomized controlled phase 2 trial. Subjects will be assigned to either placebo or alvimopan groups according to a block randomization.

Primary Objective: To determine the efficacy of alvimopan to reduce postoperative ileus in patients undergoing CRS/HIPEC, as measured by the composite of time to recovery of upper and lower GI function.

Treatment Description: Alvimopan (12 mg) or Placebo 30 minutes – 5 hours prior to surgery, then twice daily (BID) starting POD 1 for a maximum of 7 days or until hospital discharge.

Primary Endpoint(s): Time to either 1st solid food or 1st bowel movement postoperatively, whichever is later.

Study Stopping Rules:

At accrual of 64 patients, a futility analysis will be performed. If the conditional power (as computed for log-rank tests) is less than 10% at this halfway point, we will suspend the study. The conditional power threshold of 10% was chosen based on boundaries set in Jennison and Turnbull, as well as with consideration to the probability of stopping early based on a series of effect sizes. If the null hypothesis is true (i.e. a hazard ratio of 1), the study will stop early at the interim to fail to reject the null hypothesis 69.49% of the time. Under the alternative hypothesis, the study will stop early 10.35% of the time while maintaining a type II error rate of 20%.

### 3. Report Overview

The purpose of this report is to review cumulative enrollment and safety data for the subjects enrolled in the ILEUS study. This report reflects data from the study database as of xxx. Within the body of the report are summary tables of enrollment, demographic characteristics, and adverse events. Readers of this report are asked to maintain the confidentiality of the information provided in this report.

### 4. Quality Management

4.1 This study was monitored by the UCSD Moores Cancer Center CTO xxxxx  
Protocol deviations/violations:

4.2 Protocol deviations

### 5. Methods – Data Set

This report is based on all data downloaded on xxxx from the VELOS portal (<https://velos.ucsd.edu>).

### 6. Participant Status

This section summarizes the participant status and enrollment by study month. Enrollment is defined as received at least one treatment.

Study Month	Year & Month	N Subjects Enrolled
1		
2		
3		

XX Subjects have been consented. This trial is accruing at a rate of X subjects per month.

### 7. Subject Consent and Treatment Dates

Consent and Treatment Dates

Subject ID	Consent Date	Treatment Start Date

## 8. Screen Failures

This study having two time points where subjects potentiality may fail to initiate (screen fails) or continue treatment (surgical fails). Subjects with a surgical failure will be followed since they are in both the safety and IIT populations.

### 8.1 Screen Failures

Subject ID	Consent Date	Screen Failure Date	Reason for Screen Failure

### 8.2 Surgical Failures

Surgical Failures are still in the intent to treat and safety populations since they were randomized and received at least one dose of medication.

Subject ID	Consent Date	Surgical Failure Date	Reason for Surgical Failure

## 9. Early Discontinuation/Off Treatment

### 9.1 Completed Treatment

Subject ID	Off Treatment Date	Off Treatment Reason

### 9.2 Early Discontinuation

Subject ID	Off Treatment Date	Off Treatment Reason

## 10. Demographics

This section includes the key demographics for the treated subjects, including surgical failures.

Categorical measures:

- Gender
- Race
- Ethnicity

Continuous measures:

- Age (years)

Continuous variables are summarized with N, mean, standard deviation, median.

Categorical variables are summarized using frequency tables and percentages

Gender, Race, Ethnicity

	Frequency	Proportion
Gender		
Female		
Male		
Race		
White		
Black, African- American		
Asian		
Native America		
Unknown or Not Reported		
Ethnicity		
Non-Hispanic		
Hispanic		

Continuous measures: Continuous variables are summarized with N, mean, standard deviation, median.

Age (years)

	N	Mean	SD	Median
Age				

Demographic Information for All Consented Subjects

Subject ID	Age	Gender	Ethnicity	Race

**11. Stopping Rules**

At accrual of 64 patients, a futility analysis will be performed.

**12. Deaths**

Subject ID	Date of Death	Reason for Death	On Treatment?

**13. Post-Treatment Adverse Events**

**13.1 Adverse Events Summary**

Severity	N Adverse Events
Mild (grade 1)	
Moderate (grade 2)	
Severe (grade 3)	
Life-threatening (grade 4)	

Severity	N Adverse Events
Fatal (grade 5)	
Total	

### 13.2 AE by Grade

### 13.3 AE by relationship

Note: A list of all adverse events is in Appendix A. These are all AEs; SAEs are also reported in next section.

### 13.4 Serious Adverse Events

#### Serious Adverse Events

Patient Study ID	Serious Adverse Event Name	Severity/Grade	Start Date	Stop Date	Attribution

### 14. Software

Statistical software R (version 3.1.3) is used <http://www.r-project.org>.

### Appendices

- 1 Adverse Events
- 2 Treatment Assessment
- 3 Response Assessment
- 4 Issues with data

BSR data checks include verification of doses, number of appropriate drug and response cycles based on treatment start date, redundant and/or missing data, and other data elements as needed based on study protocol.

## **Appendix D. UCSD Moores Cancer Center Data Monitoring Plan**

### **Introduction**

This data reporting plan outlines the routine monitoring reports that are to be generated by the study statistician or the study data manager, based on the data that have already been entered into the electronic data capture data base (VELOS).

The purposes of these reports are to monitor the progress of trials and the safety of participants, to assure data accuracy, data completeness and protocol compliance.

All the study personnel listed on the VELOS Clinical study information and personnel contact information page will receive these reports. (see Appendix A).

For an outline of the report see Appendix B.

### **I. Table of Contents**

#### **II. Executive Summary –**

The Executive Summary will be an overarching description of the data analyzed.

#### **III. Protocol Synopsis -**

The Protocol will be an overarching description of the study.

(note: Study coordinator is to obtain this information from the research plan and the first page of IRB submission for this report. It may be also available on the VELOS study information page.)

#### **IV. Study Data Report –**

The Study Report will include the following Tables:

- Table 1: Overall Enrollment
- Table 2: Monthly Enrollment
- Table 3: Consent and Treatment Dates
- Table 4: Screen Failures
- Table 5: Early Discontinuations/Off Treatment
- Table 6: Gender, Race, Ethnicity
- Table 7: Age (years)
- Table 8: Subjects Demographics
- Table 9: Deaths
- Table 10: Adverse Events Summary
- Table 11: Serious Adverse Events
- Appendix: Listing of All Adverse Events

The Principal Investigator will receive additional tables in regards to study treatment, response assessment and data completeness as outlined in sections 5-8 below. Additional tables related to stopping rules will be added in the interim futility report. These may include unblinded randomization tables, as well as, response assessments.

Only, the Principal Investigator will received reports of outcome data and appendices that include treatment assessment, response assessment, baseline characteristics and data issues, as determined by study statistician.

Below has details for each of the tables/reports listed above. The frequencies of running the reports was determined by the study protocol. Note: This is a double blind study. All reports, except futility and final, will contain aggregated data.

### 1. Overall Enrollment - Table 1

- Purpose

To monitor enrollment; to ensure that accrual goals are met in a timely manner; to notify the team when accrual goal is nearing completion

- Components

Accrual (number of patients and percentages) by month.

- Frequency: first two week data analysis, futility, semi-annually, annually

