#### **10.4 Data and Safety Monitoring/Auditing**

Data and Safety reporting will be supported by the study statisticians according to the attached monitoring plan (Appendix C and D). A series of comprehensive safety and data monitoring reports will be generated every six months for review by the study team in addition to the annual DSMB report described below.

In addition to adverse event monitoring and clinical oversight by the principal investigator and co-investigators, quality assurance of the study will be performed by the clinical trials office internal monitor. Monitoring intervals will be dependent upon the number of patients enrolled and the complexity of the study.

This study will also use the UCSD Moores Cancer Center Data Safety and Monitoring Board (DSMB) to provide oversight in the event that this treatment approach leads to unforeseen toxicities. Data from this study will be reported annually and will include:

- 1) the protocol title, IRB protocol number, and the activation date of the study.
- 2) the number of patients enrolled to date
- 3) the date of first and most recent patient enrollment
- 4) a summary of all adverse events regardless of grade and attribution
- 5) a response evaluation for evaluable patients when available
- 6) a summary of any recent literature that may affect the ethics of the study.

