### 5. Stopping Rules (Tables may vary)

- Components: adverse events reported to the investigator by participants.

- Tables of response times for either 1st solid food or 1st bowel movement, whichever is later.
- Frequency: first two week data analysis, futility, semi-annually, annually
- NA

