## Timeline for Reports

Date	Accrual*	Study Status	Baseline Characteristics*	Study Completeness	Toxicity/Adverse Event	Treatment and Dose Modifications	Interim Analysis Response Assessment
4/17/2018	X	X	X	X	X	X	
Xxxxxx *** (futility Analysis)	X	X	X	X	X	X	X
11/21/2018	X	X	X	X	X	X	
5/1/2019	X	X	X	X	X	X	
11/1/2019	X	X	X	X	X	X	
5/1/2020	X	X	X	X	X	X	
11/1/2020	X	X	X	X	X	X	
5/1/2021	X	X	X	X	X	X	

\*Accrual and Baseline Characteristics Reports may be discontinued following closing the study to accrual

\*\*\* Futility Analysis will be completed when necessary

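### Appendix D allows unblinded tables in the interim futility report but names no closed recipient for it

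*Combined protocol and SAP*

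**What the plan says.** Section IV of Appendix D covers the content of the futility report and says of its stopping-rule tables: "These may include unblinded randomization tables, as well as, response assessments". It then lifts the usual restriction for that report: "All reports, except futility and final, will contain aggregated data".

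Two rules bear on who receives what.

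- The Appendix D Introduction gives a general rule: "All the study personnel listed on the VELOS Clinical study information and personnel contact information page will receive these reports".
- Section IV adds a narrower one: "The Principal Investigator will receive additional tables in regards to study treatment, response assessment and data completeness as outlined in sections 5-8 below". It also makes the Principal Investigator the only recipient of outcome data and of several appendices, ending with "baseline characteristics and data issues, as determined by study statistician".

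Item 5 of Appendix D (Stopping Rules) lists tables of primary-endpoint times and gives "Frequency: first two week data analysis, futility, semi-annually, annually". In the Timeline for Reports, the column headed "Interim Analysis Response Assessment" is marked only in the futility row.

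In the main protocol, Section 9.8 names the Biostatistics Shared Resource statisticians as those who run the futility analysis. Section 9.3 describes release of treatment codes once, after database lock. Section 10.4 describes six-monthly reports "for review by the study team in addition to the annual DSMB report described below" and does not mention the futility report.

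**The concern.** A double-blind trial with an interim look at efficacy needs a stated boundary between those who see results by arm and those who treat patients or decide on data. Here the plan foresees a mid-trial document that may show assignments, and no rule in it keeps that document from the blinded team.

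Section 10.8 makes the Principal Investigator personally responsible for overseeing the treatment of every patient. If that role saw arm-level interim results, three judgements could be affected:

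- the timing of discharge, since Section 2.3 censors patients discharged before GI-2, and time to the discharge order is itself a secondary endpoint;
- discretionary withdrawal under Section 5.5;
- any part that person has in the case-by-case exclusion decisions, which Section 9.3 requires to be made without knowledge of treatment.

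Even if nothing were affected, a result after a continued trial could be challenged because its own monitoring plan allowed unblinded tables without saying who may hold them.

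**Working it through.** **Step 1: look for a closed recipient.** No figure in the plan settles this, so the check is a comparison of the places where such a rule could stand.

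| Place | What it settles | What it leaves open |
|---|---|---|
| Section 9.8 | Who computes the futility analysis | Who receives the report or the conditional power |
| Section 9.3 | Code release after database lock | The earlier access that a two-arm log-rank test at the look requires |
| Section 10.4 | An annual DSMB report, including a response evaluation | Whether the DSMB sees the futility report |
| Appendix C, 3. Report Overview | Readers are asked to keep the report confidential | Who the readers are |
| Appendix D, Introduction | Reports go to all listed personnel | Any exception for unblinded content |
| Appendix D, Section IV | Outcome data and items 5-8 go to the Principal Investigator | Whether this covers randomization tables |

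None names a closed recipient.

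**Step 2: does the text send the tables to the Principal Investigator?** Pointing that way: this role receives items 5-8; item 5 is Stopping Rules and lists futility in its frequency; outcome data go only to this role; and the timeline marks response assessment in the futility row. Pointing the other way: unblinded content is only permitted; the statistician has a say in content; item 5 ends with a not-applicable entry; and items 6-8 do not list futility in their own frequencies. So receipt is an inference. The gap does not depend on it, because the alternative in the Introduction is wider circulation.

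**Step 3: how many later assignments could be learned?** Section 9.1 uses blocks of 4, so 64 IDs make 64/4 = 16 complete blocks. A listing of exactly those IDs reveals no later assignment. A listing that runs into an open block fixes at most 2 more. Any ID awaiting reassignment after a screen failure would add to this; the documents give no number.

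A listing of all randomized patients would also show the arms of those still in hospital. With the 10-day median stay (Section 1.1) used as an average and 40 patients a year (Section 9.2), that is 40 × 10/365 = 1.1 patients. At the full 60-70 procedures a year it is 1.6-1.9.

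**Step 4: illustrative effect on type I error.** Assume 122 events, 61 in each half, and a null treatment effect. Suppose k of the 64 second-half assignments are known, the rest are guessed at 50%, and knowledge shifts the hazard ratio towards alvimopan by an assumed 1.1 to 1.3. The shift in the second-half statistic is

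d = ln(HR) × (√61/2) × (k/64).

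For HR 1.3 and k = 2: 0.262 × 3.905 × 0.03125 = 0.032. The final statistic moves by 0.032/√2 = 0.023, so without a futility stop the error is 1 − Φ(1.645 − 0.023) = 5.24%. For k = 4 (about the two from an open block plus up to 1.9 in hospital), d = 0.064 and the error is 5.48%.

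With a binding futility stop, the trial continues only if the interim statistic is at least b:

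| Futility rule | b | No bias | k = 2, HR 1.1-1.3 | k = 4, HR 1.1-1.3 |
|---|---|---|---|---|
| No stop | none | 5.00% | 5.1-5.2% | 5.2-5.5% |
| Conditional power below 20%, current trend | 0.742 | 4.15% | 4.2-4.3% | 4.3-4.5% |
| Appendix C (69.49% stop under the null) | 0.510 | 4.5% | 4.6-4.7% | 4.6-4.9% |
| Conditional power below 20%, design HR 1.59 | −0.326 | 4.96% | 5.0-5.2% | 5.1-5.4% |

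The largest rise is 0.24 percentage points for k = 2 and 0.48 for k = 4.

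**The case against.** The strongest reply is that no disclosure is established. The wording is permissive, the statistician has a say in content, and the sentence on stopping-rule tables is separate from the one giving tables to the Principal Investigator. Randomization tables might be counts by arm, which would identify nobody. A separate access procedure may exist outside these documents: the Appendix D Introduction refers to a personnel list and a report outline in appendices that the documents do not show under those labels. All of this stands as a limit on certainty. A reader might infer that the plan unblinds the Principal Investigator at the look, or that no firewall exists anywhere. The documents support neither; they support only that none is stated.

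The second reply is that the harm is small. The pharmacy carries out randomization and capsules are over-encapsulated. GI-2 requires a bowel movement and is timed from a patient diary, with at least 10% audited. Section 4.1 ties discharge to GI-2, so discharge before it should be the exception. Under the current-trend and Appendix C boundaries, type I error stays below 5% throughout. This also stands. It argues against calling the trial's error rate compromised, but it does not supply the missing recipient.

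**Conclusion.** The point holds as a gap in the monitoring plan that should be closed before the futility look. Confidence is high that the text names no closed recipient and does not describe interim code access. It is lower on what would happen in practice.

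The risk is to blinding and credibility. A reader might infer serious bias in the hazard ratio. The documents do not show that, nor which way any effect would run. The figures above rest on assumed shifts towards alvimopan, an assumed number of known assignments and a subject-level listing; at most they move the error rate by about half a percentage point.

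**What to change.** - **Appendix D, Section IV:** state that the unblinded futility report goes only to the Biostatistics Shared Resource statisticians who run the analysis and to the existing Moores DSMB. The Principal Investigator and study team are told only *continue* or *stop*.
- **Appendix D, Introduction, item 5 and Timeline for Reports:** align the general distribution rule, the Stopping Rules item and the futility row with this, and mark that row as a closed report.
- **Section 9.3:** state that this is the only access to treatment codes for efficacy analysis before database lock.

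If a separate access procedure already exists, citing it in both places would serve, provided that it sets the same limits.

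The cost is a wording amendment, which needs IRB approval under Section 10.6, and one ad hoc DSMB review. That review slightly widens the board's role, which Section 10.4 describes as oversight of unforeseen toxicities with annual reporting. No endpoint, test or sample size changes.

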### **1.2 Study Agent**

Alvimopan is an oral peripherally-acting mu opioid receptor antagonist, with limited ability to cross the blood-brain barrier. There have been eight randomized-controlled trials published in English language journals documenting the safety and efficacy of alvimopan for postoperative ileus.

From a safety standpoint, a meta-analysis of all randomized controlled trials found the

most common adverse events with alvimopan included nausea, vomiting, constipation, flatulence, distension, headache, and pruritis (all greater than 10% in incidence). Rates of all common AEs from this meta-analysis is listed in the table below.

Adverse Event	Rate (%) 
Nausea	56.1
Vomiting	18.3
Constipation	15.4
Flatulence	14.5
Distension	12.2
Headache	11.2
Hypotension	8.5
Hypertension	9.4
Pyrexia	9.9
Pruritis	11.7
Tachycardia	7.1
 Among patients receiving 12 mg alvimopan dose	

It is worth noting that most of the GI-related adverse events are also symptoms of postoperative ileus, making attribution to alvimopan imprecise. Furthermore, many AEs were significantly lower in the alvimopan groups than the placebo groups (nausea, vomiting, constipation, and pyrexia). The remaining common AEs were no different in the alvimopan and placebo groups.

Serious adverse events were reported in 3-25.7% of participants in RCTs, and included infection, anastomotic leak, dehiscence, pain, postoperative ileus, dehydration and small bowel obstruction. In all trials reporting SAEs, the rate in the alvimopan group was equal to or less than in the placebo group, and no trials reported deaths attributed to alvimopan.

One study investigating 0.5 mg twice daily alvimopan for 12 months for the treatment of opioid-induced bowel dysfunction found a higher incidence of myocardial infarction in the alvimopan group. The events occurred 1-4 months after the start of treatment, and the increased risk of MI has not been observed in other studies with shorter duration (7 days) of alvimopan in postoperative patients. A large matched-cohort study using a national inpatient database including 7050 patients found a *lower* risk of cardiovascular morbidity in the alvimopan cohort than in the control cohort (19.4% vs. 24.0%,  $p = 0.0001$ ).

Alvimopan has been found to decrease the time to return of bowel function and time to discharge in multiple randomized controlled trials, as seen in the table below.

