### 4. Toxicity/Adverse Event Report – Tables 9-11 and appendix

- Purpose:

To monitor toxicities; to evaluate unexpected toxicities; to ensure that toxicity rates are acceptable. All participants receiving investigational agents will be evaluated for safety.

- Components: adverse events reported to the investigator by participants.

- 1) Listing of all deaths.
- 2) Frequency tables of all the signs and symptoms or laboratory toxicities by grade and across grades
- 3) Listing of all adverse events. The list will include patient number, toxicity name, severity/grade of reaction, relationship to study drug.

- Frequency: first two week data analysis, futility, semi-annually, annually

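### No report planned for the DSMB shows adverse events by treatment arm, so the board has no written means of separating a drug effect from surgical morbidity

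*Combined protocol and SAP*

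**What the plan says.** Section 10.4 engages the cancer center's DSMB "to provide oversight in the event that this treatment approach leads to unforeseen toxicities". It places data and safety reporting under Appendices C and D, with reports "every six months for review by the study team in addition to the annual DSMB report described below". The DSMB report has a six-item content list. Its safety item is "a summary of all adverse events regardless of grade and attribution", with no mention of treatment arm.

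Appendix D (IV. Study Data Report) gives the rule on blinding: "This is a double blind study. All reports, except futility and final, will contain aggregated data". Its AE report (item 4) has among its purposes "to evaluate unexpected toxicities; to ensure that toxicity rates are acceptable" and is run at the first two-week analysis, at futility, semi-annually and annually. The recipients Appendix D names are study personnel and the Principal Investigator. It does not name the DSMB.

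The Appendix C templates for deaths (12), AE counts by grade (13.1) and SAEs (13.4) have no arm column. The SAE listing shows event, grade, dates and attribution.

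Section 9.3 has the statistician request the treatment codes after database lock. Section 9.9 plans a comparison of AEs between arms but sets no mid-trial look for the board. Section 7.6.1 sends expedited notices to the Principal Investigator and the HRPP.

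**The concern.** A safety board in a placebo-controlled trial adds most when it can compare arms, because the study team is blinded and cannot. That matters here for three reasons the protocol itself gives. Background morbidity is high: section 1.1 puts severe morbidity after CRS/HIPEC at 16%. Section 1.3 says no study of alvimopan after this operation has been published. Section 1.2 says most GI adverse events are also ileus symptoms, so attributing them to alvimopan is imprecise; attribution in the listings therefore cannot stand in for a comparison.

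Without an arm split, an excess of events on alvimopan can look like ordinary surgical morbidity. A fall in ileus-related events on alvimopan could also offset a rise in other events within the same pooled total. Keeping the study team blind does not require keeping the DSMB blind.

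**Working it through.** The plan states no figure to reproduce on this point. The check is a reading of the text followed by an illustration.

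**Text, side by side**

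| Question | What the documents give |
|---|---|
| Which reports are pooled? | All except futility and final (Appendix D, IV) |
| Does this reach the DSMB report? | By inference: 10.4 puts safety reporting under Appendices C and D, and the Appendix D tables are also run annually. Section 10.4 does not itself say pooled |
| Do the templates carry arm? | No (Appendix C, 12, 13.1, 13.4) |
| When are codes requested? | After database lock (9.3) |
| Is there a mid-trial exception? | The futility report. The AE report is run then too (Appendix D, item 4 and timeline), but the tables described as additions concern stopping rules, randomization and response |
| Is a closed report, an A/B table or a DSMB route to the codes described? | No |

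**Illustration (arm rates are assumptions)**

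Inputs: 1:1 allocation (9.1); 16% severe morbidity (1.1), used as a placebo rate; an assumed doubling to 32% on alvimopan; accrual of 40 a year (9.2).

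1. Pooled rate under 1:1 = (p_alvimopan + p_placebo)/2. For 32% and 16% this is (32 + 16)/2 = 24%. For 24% in both arms it is also 24%. The two situations give the same expected pooled table.
2. What a pooled table can show. Section 1.2 says: "Serious adverse events were reported in 3-25.7% of participants in RCTs". Take the upper end, 25.7%, purely as a marker. The probability that the pooled rate exceeds it, from the sum of two binomial counts with n/2 patients each, is:

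| Arms (placebo/alvimopan) | n = 40 | n = 64 | n = 80 |
|---|---|---|---|
| 16% / 32% | 35.7% | 35.9% | 35.8% |
| 24% / 24% | 35.9% | 36.1% | 35.9% |
| 16% / 16% | 4.5% | 2.1% | 1.3% |

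The first two rows agree by construction, since they share a mean. They show that pooled data cannot say which arm carries the events. The third row shows that pooled data are not empty: if 16% is trusted as background, a rise is more likely to be noticed. Its cause (drug, case mix, or a background rate other than 16%) stays unknown.

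3. What a by-arm table would add. At 64 patients, expected events are 32 × 0.16 = 5.1 and 32 × 0.32 = 10.2. A split of 5 v 10 of 32 gives one-sided Fisher p = 0.12. Power for 16% v 32% with 32 per arm is about 44% (one-sided 0.05).
4. Timing. The first annual report would cover about 40 patients (40/128 = 31%) and the second about 80 (80/128 = 63%), with the futility look at 64 between them.

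**The case against.** The strongest reply is that pooling of the DSMB report is inferred. The aggregation sentence sits in an appendix whose named recipients are study personnel, and it does not define aggregated. Section 10.4 gives the DSMB report its own list, and the two sets of rules differ elsewhere: Appendix D sends outcome data only to the Principal Investigator, while the DSMB list includes a response evaluation. The board is a standing one, and nothing in these documents forbids it from asking for codes. This stands as a limit on certainty. It does not supply a by-arm report, because none is written anywhere.

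A reader might infer that the board sees only one pooled AE count a year. The documents do not support that. If Appendices C and D govern its report, it also receives listings of deaths with reason, of SAEs with grade, dates and attribution, and of all AEs with relationship to drug. A novel or striking event could be recognised case by case from these.

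A reader might also infer that toxicity cannot be judged at all during accrual. That goes too far as well. The futility report is exempt from pooling and coincides with an AE report, so one by-arm look is possible, though not stated. Nor do the matching 36% figures show that pooled data are uninformative, as the 16%/16% row makes clear.

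Finally, the doubling is hypothetical. Section 1.2 reports SAE rates on alvimopan equal to or below placebo in every trial that reported them. Moreover, 25.7% is an SAE figure from trials in other operations, not the same quantity as the 16% and not a threshold in this plan. Both points stand, which is why the figures serve only as illustration.

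**Conclusion.** The concern holds in this form: as written, no report planned for the DSMB shows adverse events by arm, so the board could not separate a drug effect from surgical morbidity using its planned reports. The futility report near 64 patients is a possible exception, but the plan states neither an AE split nor delivery to the board.

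The conclusion rests on reading aggregated as pooled across arms, which the link to double blinding in the same statement supports, and on 10.4 bringing the DSMB report under the appendices. It does not depend on the assumed rates. Their role is to show that one pooled value, such as 24%, is compatible with equal arms or with a doubling, while a rise above a trusted 16% would be visible without its cause. The change is worth making, but at these sample sizes it would improve the board's view rather than guarantee detection.

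**What to change.** 1. In Appendix D and section 10.4, limit the aggregated-data rule to reports for study personnel and the Principal Investigator.
2. Add to the existing annual DSMB report, and to the futility report, a closed section for the DSMB only, with deaths, SAEs, AEs and discontinuations by masked arm (A/B). The Biostatistics Shared Resource statisticians who already run the futility analysis (9.8) can prepare it. The six-monthly cycle belongs to the study team, so the board's annual cycle is the one to use.
3. State that the DSMB may request the treatment codes.
4. Amend section 9.3, which has codes requested only after database lock, to allow this. The futility log-rank test also needs arm assignments before lock, so the same amendment can cover it.

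The cost is a wording change and existing tables split by arm for one recipient. The downside is that a statistician would hold the arm codes from the first annual report (about 40 patients) rather than from the futility analysis (64). The board should also be told that by-arm differences at these sizes are imprecise.
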